2.3 Primary Endpoint

Proportion of patients who achieve CR or PR by day 28 of treatment with itacitinib without the addition of any other systemic GVHD treatment including steroids.

CR is defined as absence of GVHD symptoms. PR is defined as improvement in one or more organs involved with GVHD symptoms without progression in other organs. For a response to be scored as CR or PR on day 28, the patient must be in CR or PR on day 28 and have had no intervening systemic therapy for acute GVHD other than itacitinib.

Secondary endpoints:

- Cumulative incidence of steroid-refractory GVHD (defined as GVHD that worsens (increase by one or more grade) after 3 days, or fails to respond to treatment within 7 days (for GVHD grade III) or 14 days (for GVHD grade II) or 2nd line therapy beyond systemic steroid treatment is begun within 28 days of starting steroids.
- 2. Distribution of maximal GVHD grade (I-IV) by day 28 after starting treatment with itacitinib
- 3. Cumulative incidence of serious infections (defined as bacteremia, CMV infection needing treatment, EBV infection needing treatment, or invasive fungal infection)
- 4. Overall survival at 6 and 12 months
- 5. Cumulative incidence of NRM at 6 and 12 months
- 6. Relapse rate at 6 and 12 months
- 7. Cumulative incidence of chronic GVHD requiring systemic steroid treatment by one year from enrollment

8. Cumulative steroid dose (over 4 weeks) in patients who receive steroids as second line therapy

Safety endpoints

1. Number and proportion of patients developing reportable AEs and SAEs according to relatedness to study drug and stratified by severity

Exploratory endpoints

1. GVHD biomarker concentrations (ST2 and REG3) and their associations with clinical endpoints at day 28 after starting treatment with itacitinib

The two hypotheses are: 1) that GVHD biomarkers will remain low in study patients who respond to itacitinib treatment, but will rise in non-responders and (2) biomarker concentrations will be equivalent to those in historical control patients who respond to steroid treatment for low risk GVHD.

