5.7 Duration of Follow-Up

Patients will be followed until 1 year post-enrollment, withdrawal of consent or until death, whichever occurs first. HCT patients are followed closely and frequent clinical evaluations are the norm. While the following outlines the minimum frequency of follow-up evaluations, it is anticipated that the majority of patients will be evaluated more frequently.

During the first 4 weeks of participation (i.e., through the last dose of the first cycle of itactinib), patients will be seen at least weekly for assessment of their GVHD. During the second four weeks (i.e., the maintenance cycle of itacitinib), patients should be seen at least every other week, although it is anticipated that most patients will be seen more frequently, i.e., weekly. Patients will be evaluated at least at three, six and twelve months from treatment initiation.

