6.2 Follow-Up Procedures

The following outlines the minimum frequency of follow-up evaluations, it is anticipated that the majority of patients will be evaluated more frequently.

During the first 4 weeks of participation (i.e., through the primary endpoint), patients will be seen at least weekly for assessment of their GVHD. During the second four weeks patients should be seen at least every other week, although it is anticipated that most patients will be seen more frequently, i.e., weekly. Patients will also be evaluated at study day 86 (30 days from completion of treatment). In addition, relapse, survival, and chronic GVHD will be reported at six and twelve months from treatment initiation.

Infections, as defined in sections 7.2.3 to 7.2.5 will be closely monitored on this study. In our preliminary data (section 1.2), 100% of CMV infections requiring treatment developed within 90 days from starting systemic GVHD treatment, 100% of EBV infections requiring treatment, 85% of bacteremia, and 75% of invasive fungal infections. All patients who developed at least one serious infection did so within 90 days. Given these data, we will monitor for serious infections from start of itacitinib treatment through study day 90.

Follow-up studies are detailed in the Time and Events Table below.

	CALENDAR BASED ASSESSMENTS											
	Screening	Study day 0	Study day 7	Study day 14	Study day 21	Study day 28 ¹	Study day 42	Study day 56	Study day 90	Study day 180	Study day 365	GVHD Flare ⁷
Windows	Newly diagnosed acute GVHD in need of systemic treatment +/- 1 day	Within 4 days of Ann Arbor Score Notification	+/- 2 days	+/- 2 days	+/- 2 days	+/- 1 day	+/- 3 days	+/- 3 days	+/- 5 days	+/- 14 days	+/- 14 days	+/- 3 days
Eligibility Review	х											
Concomitant Medication Review ²	х	х	х	х	х	х	х	х	х			
Adverse Event Evaluations ³	х	Adve	erse event	s will be rep	orted from s Report seri	study day 0 ous adverse	through 30 e events as	days after t they occur.	he last dos	e of study dru	g.	
Infections		Infec	tions as d	efined in se	ctions 7.2.3	-7.2.5 will be	e reported f	rom study c	lay 0 throug	gh study day 9	00	
Serum Chemistry	Х											
GVHD Staging ⁴	Х	Х	х	х	х	х	х	х	х			х
Itacitinib			200 mg daily induction cycle 200 mg daily maintenance cycle (responders only) ⁵									
Survival, Relapse & Chronic GVHD Status										х	х	
	CORRELATIVE STUDIES											
5 ml serum ⁶	Х	Х	Х	х	х	х						х

¹ The primary endpoint is assessed on day 28 ±1 day

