7.1.8 Relapse

Relapse, including date of relapse, of the underlying malignancy will be recorded.

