11.3 Data Analysis Plans

The primary endpoint is the proportion of patients who achieve CR or PR by day 28 of treatment with itacitinib without the addition of any other systemic GVHD treatment including steroids. Death, lack of GVHD response to itacitinib by day 28 of treatment, or initiation of steroid or other systemic immunosuppressive therapy for GVHD will be considered failures for this endpoint. The proportion of patients who achieve CR or PR by day 28 in the study patients will be compared to the historical control rate of 67%.

Secondary outcomes such as cumulative incidence of steroid-refractory GVHD, proportion of patients with maximal grade I, II, III, and IV GVHD by day 28 after starting treatment with itacitinib, cumulative incidence of serious infections, cumulative incidence of hematologic toxicities, cumulative steroid dose over four weeks in patients who fail itacitinib monotherapy, overall survival at 6 and 12 months, cumulative incidence of NRM at 6 and 12 months, relapse rate at 6 and 12 months, and cumulative incidence of chronic GVHD requiring systemic steroid treatment by one year will be estimated and compared to historical controls.

Continuous variables will be summarized using standard summary statistics such as number of observations (n), mean, standard deviation (SD), minimum and maximum values, median, and 1st and 3rd quartiles. Categorical variables will be summarized in frequency tables as counts and percentages.

Cumulative incidence of non-relapse mortality will be estimated by Gray's method⁵³ and relapse will be considered as a competing risk. Disease free and overall survival, defined as the time from the transplantation to death or to last follow-up if alive, will be estimated by the method of Kaplan-Meier and the probability curves and 95% confidence intervals will be provided based on the method of Brookmeyer and Crowley⁵⁴.

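### Section 11.3 gives disease-free survival the overall-survival event (death only), so relapse never counts and the two curves coincide

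*Combined protocol and SAP*

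**What the plan says.** The last paragraph of section 11.3 deals with both survival measures in one sentence: "Disease free and overall survival, defined as the time from the transplantation to death or to last follow-up if alive", and both "will be estimated by the method of Kaplan-Meier and the probability curves and 95% confidence intervals will be provided". Origin, event and censoring are stated once, for the pair. This is the only place in the documents where disease-free survival appears.

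Relapse is handled elsewhere:

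- In the NRM sentence just before it in section 11.3, "relapse will be considered as a competing risk".
- Section 2.3 lists "Relapse rate at 6 and 12 months" and, separately, "Overall survival at 6 and 12 months" as secondary endpoints. DFS is not listed there or in section 11.1.
- Section 7.1.8 states: "Relapse, including date of relapse, of the underlying malignancy will be recorded".
- Section 6.2 states that "relapse, survival, and chronic GVHD will be reported at six and twelve months from treatment initiation".
- Section 5.7 fixes the observation period: "Patients will be followed until 1 year post-enrollment, withdrawal of consent or until death, whichever occurs first".

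**The concern.** A measure called disease-free survival should end at recurrence of the disease. Under the rule in section 11.3, relapse neither ends the interval nor stops follow-up; only death does. A literal reading produces two curves with different names and the same content, and the one labelled disease-free includes patients whose disease has returned.

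What is at stake is one reported analysis. A reader of the results would take the DFS figure to reflect relapse when it does not, and the figure would be too high by the proportion of patients alive after relapse. If the definition were corrected only after the data had been seen, the choice of definition would be post hoc.

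**Working it through.** The documents give no DFS rate, event count or power, so there is no plan figure to reproduce. The check applies the rule literally and then sizes the consequence.

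**Step 1: the rule applied to four kinds of patient** (times are illustrative)

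| Patient | DFS as written | DFS with relapse or death as event |
|---|---|---|
| Relapse month 4, alive month 12 | event-free, censored month 12 | event month 4 |
| Relapse month 4, death month 9 | event month 9 | event month 4 |
| Non-relapse death month 5 | event month 5 | event month 5 |
| No relapse, alive month 12 | censored month 12 | censored month 12 |

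The middle column is also the OS record for each patient. Identical times and event indicators give identical Kaplan-Meier curves. Only patients who relapse are scored differently, and at 12 months only those alive after relapse differ in status.

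**Step 2: formula for the overstatement at 12 months**

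Let r be the relapse incidence, a the share of relapsed patients alive at 12 months, and m the NRM, all from the same origin and with complete follow-up.

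- OS, and DFS as written: 1 − m − r(1 − a)
- DFS with relapse or death as event: 1 − m − r
- Difference: r × a

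NRM cancels from the difference, so no value of m is needed to size it.

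**Step 3: inputs**

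- N = 70: section 11.2.
- r = 10%, 20%, 30%: assumed, because the documents give no relapse rate.
- a = 30%, 50%, 70%: assumed, because the documents do not give it.
- m = 9%: the six-month NRM in section 8.7, carried to 12 months only to show levels.

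**Step 4: results** (overstatement in percentage points, with patients out of 70)

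| r | a = 30% | a = 50% | a = 70% |
|---|---|---|---|
| 10% | 3 (2.1) | 5 (3.5) | 7 (4.9) |
| 20% | 6 (4.2) | 10 (7.0) | 14 (9.8) |
| 30% | 9 (6.3) | 15 (10.5) | 21 (14.7) |

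Middle case with m = 9%: as written, 1 − 0.09 − 0.20 × 0.50 = 0.81; with relapse as an event, 1 − 0.09 − 0.20 = 0.71. The gap is 0.10, and 0.10 × 70 = 7 patients.

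**Step 5: Kaplan-Meier check by simulation**

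There were 7,000 simulated patients with exponential times: NRM set to 9% and relapse to 20% at 12 months, a median of six months from relapse to death, and censoring at 12 months. OS and DFS as written had the same time and event for every patient, and both curves gave 0.826 at 12 months. DFS with relapse or death as the event gave 0.728. The gap of 0.098 is close to the middle case above.

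**The case against.** **The definition may belong to OS alone.** The wording is a standard OS definition and directly follows that term. The grammar, however, covers both measures. If it did attach to OS only, DFS would have no definition anywhere and the duplicate curve would not follow, but the sentence would still need correcting.

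**DFS carries little weight in this trial.** This stands. DFS is not an objective and not an endpoint in section 2.3 or 11.1. Section 11.2 rests the phase III decision on response rate, steroid-refractory GVHD, NRM and serious infections. DFS does not enter the sample size, the futility boundary or the stopping rules in section 8.7.

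A reader might infer three stronger points that the documents do not support:

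- *That the trial cannot see a relapse effect.* Relapse at 6 and 12 months is its own secondary endpoint, and section 11.3 plans to compare it with historical controls. The blindness is confined to the DFS curve.
- *That DFS was planned to show whether the new strategy costs disease control, and would flatter itacitinib against historical DFS.* The documents give DFS no purpose. The outcomes that section 11.3 names for historical comparison include OS, NRM and relapse but not DFS. That list is introduced as examples, so such a comparison is not ruled out, but none is specified.
- *That most records are scored wrongly.* Only relapsed patients are affected. With 20% relapse, the other 80% get the same value under either rule.

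**Conclusion.** Wrong as written. Section 11.3 omits relapse from the DFS event, so DFS duplicates OS and patients alive after relapse count as disease-free. That conclusion follows from the text and needs no assumption beyond reading the shared definition as shared.

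The size does rest on assumptions. The range of 3 to 21 points, and the middle case of 10 points, depend on relapse and post-relapse survival figures that the documents do not supply. The 81% and 71% levels also depend on using the six-month NRM at 12 months; the gap between them does not.

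The effect is limited to this one reported analysis. The primary endpoint, the monitoring rules and the separate relapse endpoint are untouched.

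**What to change.** In section 11.3, replace the joint definition with two:

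- **OS:** time to death from any cause, censored at last follow-up if alive.
- **DFS:** time to the earlier of relapse (the date recorded under section 7.1.8) or death from any cause, censored at last follow-up if alive without relapse.

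Alternatively, delete DFS, which is equally coherent because it is not among the endpoints in section 2.3 or 11.1.

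If DFS is kept, add a line on patients who enrol with persistent malignancy. Section 3.2.2 excludes them only when the disease requires withdrawal of systemic immune suppression, so some may enter, and a relapse-or-death rule does not by itself say how to score them. The time origin in the same sentence is a separate matter, but both definitions should state it.

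The cost is a sentence or two of text. No new data are needed, since the relapse date and the six- and twelve-month status are already collected. The small downside is that the reported DFS becomes less favourable. The change should be made before the analysis.

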12.0 DATA AND SAFETY MONITORING

The safety of subjects is paramount and supersedes all other concerns. This study employs several layers of oversight to ensure that patient safety is protected.

- 1. The local Data and Safety Monitoring Committee (DSMC) at each site which will be responsible for reviews of patient data at each site
- 2. The Protocol Data and Safety Monitoring Committee (DSMC), composed of the individual site PI's which will review all facets of study conduct at all sites on monthly webinars

- 3. The Tisch Cancer Institute Data and Safety Monitoring Committee (TCI DSMC) of the Mount Sinai Health System is the DSMB of record for this study. The DSMB will be compliant with the NIH approved DSMP Charter. This committee will be responsible for monitoring the safety and data integrity of the trial. It is a DSMB entirely composed of members with no connection to this clinical trial.
- 4. Annual reviews and safety reporting will be provided to the IRBs at each participating site, the Mount Sinai Health System, and the FDA as required by IND regulations (21 CFR 312.3).

This study will enroll adolescent patients who we expect will provide up to 20% of the study subjects. These patients will be enrolled from pediatric HCT centers and will receive their care from trained pediatric HCT physicians. We will closely monitor toxicity and efficacy in patients <18 years of age. The oversight boards (Protocol DSMB and TCI DSMC) can halt pediatric accrual to the study if an unexpected safety concern develops in children, while continuing adult accrual.

Protocol DSMB: The centers participating in this study are collaborating centers in MAGIC (Mount Sinai Acute GVHD International Consortium). The local site principal investigator, data manager, and study coordinator participates in monthly webinars where all facets of study conduct are discussed, thereby providing an additional layer of safety oversight.

The MAGIC Data Coordinating Center is responsible for collating all data and safety reports from all the participating sites, and providing the information to the TCI Data Safety Monitoring Committee.

TCI DSMC: The TCI DSMC serves as the data and safety monitoring board (DSMB) for investigator initiated studies conducted under the auspices of the Tisch Cancer Institute (TCI) at the Mount Sinai Health System. It is compliant with the National Institutes of Health and National Cancer Institute charter for DSMBs. This board will be responsible for monitoring the safety and data integrity of the trial. It is a DSMB entirely composed of members with no connection to this clinical trial.

12.1 Multisite Clinical Monitoring Procedures

This clinical study will be coordinated by the MAGIC Data Coordinating Center (DCC) of the Icahn School of Medicine at Mount Sinai. As such it will be conducted in accordance with the ethical principles that are consistent with Good Clinical Practices (GCP) and in compliance with other applicable regulatory requirements.

Prior to subject recruitment, a participating site will undergo a site initiation meeting to be conducted by the DCC. This will be done as an actual site visit, teleconference, videoconference, or web-based meeting after the site has been given access to the study database and assembled a study reference binder. The site's principal investigator and his/her study staff should make every effort in attending the site initiation meeting. Study-related questions or issues identified during the site initiation meeting will be followed-up by the appropriate DCC personnel until they have been answered and resolved.

This study will be monitored by a representative of the MAGIC Data Coordinating Center. Monitoring visits, whether remote or in person, will be made during the conduct of the study and at study close-out. The following issues will be monitored.

- Signed and dated ICF
- Adherence to the protocol
- Completeness and accuracy of study data and laboratory samples collection
- > Proper storage, dispensing and inventory control of investigational drug
- Compliance with state and local regulations

Any issues identified during these visits will be communicated to the site and are expected to be corrected by the site in a timely manner. For review of study-related documents at the DCC, the site will be required to ship, fax, or email documents to be reviewed, ensuring compliance with HIPAA and other privacy regulations.

Participating sites will also undergo a site close-out upon completion, termination or cancellation of a study to ensure fulfillment of study obligations during the conduct of the study, and that the site Investigator is aware of his/her ongoing responsibilities. At the time of the close-out any investigational agents not dispensed need to be returned as defined for the study or destroyed and accounted for properly.

13.0 QUALITY ASSURANCE AND AUDITS

The Data Safety Monitoring Board can request a 'for cause' audit of the trial if the board identifies a need for a more rigorous evaluation of study-related issues. A "for cause" audit would be conducted by the Project Manager of the MAGIC Data Coordinating Center.

A regulatory authority (e.g. FDA) may also wish to conduct an inspection of the study, during its conduct or even after its completion. If an inspection has been requested by a regulatory authority, the site investigator must immediately inform the MAGIC Data Coordinating Center that such a request has been made.

